7.2. Study Population

Study subjects are all patients identified in the HIRD with minimal exclusion criteria applied. This broad subject eligibility will ensure that the study is representative of the actual ‘real-world’ use of the product in a clinical setting.

7.2.1. Inclusion Criteria

All patients identified in the HIRD who have received a prescription for *Duavee* or E+P HRT since May 2014 (date of first commercial availability in the US), and have a baseline period (e.g., 6 or 12 months to be determined by a priori analyses) prior to their first study medicine prescription, will be included in this study. Codes for *Duavee* and specific E+P HRT products are listed in Appendix 2.

- To be included in the main analyses, patients need to be new initiators of *Duavee* or E+P HRT as evidenced by a sufficient baseline period (e.g., 6 or 12 months to be determined using a priori analyses) prior to their first study drug prescription with no prior use of either *Duavee* or E+P HRT.
- The duration of the baseline period will be determined prior to the start of the analysis. The analysis will assess the distribution of continuous enrollment prior to the first dispensing of *Duavee* among the exposed patients. Selection of a threshold will balance inclusion of as many *Duavee* users as is feasible with the need to ensure appropriate capture of baseline covariates among the included patients.
- Sub-analyses will be performed for those with either (1) use of E+P HRT (i.e., not new initiators), or (2) unopposed estrogen in their baseline period. See Figure 4 in Section [Section 7.8](#) for the flow of patients to the separate analyses.

7.2.2. Exclusion Criteria

Patients meeting any of the following criteria will be excluded from the study:

- Patients with an insufficient period of enrollment prior to their index prescription (e.g., 6 or 12 months as determined prior to the start of analysis) will be excluded. This period is necessary to determine if the patient is a new initiator of *Duavee* or E+P HRT without a history of unopposed estrogen use, and also to adequately ascertain baseline covariates/patient history;
- Patients without a uterus, i.e., males, or women for whom evidence of hysterectomy is identified prior to initiation of *Duavee* or comparator E+P HRT; and
- Patients with a history of any type of cancer in their baseline period.
- Patients for whom *Duavee*, comparator E+P HRT or unopposed estrogen are identified during the baseline period will be excluded from the main analyses. They will be evaluated in separate sub-analyses.

7.3. Variables and Measurement

7.3.1. Exposure

The analyses will identify exposure to *Duavee* or E+P HRT treatment based on pharmacy claims with applicable Generic Product Identifier (GPI) codes. A list of included products and the GPI codes is provided in Appendix 2.

E+P HRT comparator products were chosen and must have been commercially available in the US with an indication for the treatment of moderate to severe VMS associated with menopause or the prevention of postmenopausal osteoporosis.

The analyses will define exposure to *Duavee* or E+P HRT as follows: Patients will be categorized as having “current use” for *Duavee* or E+P HRT from their index date through to 30 days after the date when the supply of their last consecutive prescription is calculated to have been used. Prescriptions will be defined as consecutive if not more than 30 days has passed between the days supply of two adjacent prescriptions. Otherwise, a new treatment segment will be defined. The 30-day grace periods allow for the possibilities of intermittent inconsistent use and saving of dispensed pills, by which a patient may still be taking the medication even after exhausting the available supply from their most recent dispensing. For each patient, duration of exposure will be based upon the summation of recorded supply (in days) across all of their study treatment segments. Multiple treatment segments due to intermittent HRT use will be summed when calculating duration of exposure. The study will measure each exposure segment that occurs during the follow-up period in order to support analyses that consider duration of exposure and time since most recent exposure (defined as time from date of treatment end to censoring). Patients with long periods of follow-up that contain multiple treatment segments will be reflected in the variables of duration of exposure and time since most recent exposure.

7.3.2. Endpoints

The study will identify non-fatal and fatal events of the following types:

- Primary endpoints:
 - Endometrial cancer;
 - Endometrial hyperplasia.
- Secondary endpoints:
 - Venous thromboembolism;
 - Coronary heart disease (defined as myocardial infarction [MI] and sudden death);
 - Stroke (including transient ischemic attack [TIA]);
 - Breast cancer;

- Ovarian cancer;
- Thyroid cancer;
- Renal cancer and adenoma;
- Gastrointestinal cancer;
- Any cancer (any malignant neoplasm);
- All-cause mortality.

All endpoints are included in the EU risk management plan (RMP) for CE/BZA (*Duavive*). Estrogen-associated cancers (breast, ovarian, endometrial cancers) and endometrial hyperplasia are important potential risks in the RMP based on the medical literature for HRT and background incidence rates (IRs) in postmenopausal women. An important identified risk potentially associated with *Duavee* use is VTE because it is a known safety concern for both of the individual component products of CE/BA (i.e., CE and BZA monotherapies). According to the literature,⁶ MI and stroke are important potential risks that are associated with the use of HRT products in general. Thyroid cancer, renal cancer, renal adenoma, and gastrointestinal tract cancers are considered as important potential risks based on their elevated background incidence in postmenopausal women. All cancers are included because of their inclusion in the EU RMP for CE/BZA. All-cause mortality is included to provide context to fatal occurrences of the safety endpoints. For example, if a finding of increased fatal stroke events is observed, it could be assessed if this result coincided with an increase in all-cause mortality.

7.3.2.1. Primary Endpoints

The primary endpoints of endometrial cancer and endometrial hyperplasia are particularly challenging to identify in a claims database as neither endpoint has been extensively studied in this setting. For endometrial cancer, relevant diagnostic codes are nonspecific, including both endometrial cancers and relatively rare non-endometrial uterine cancers. While a claims data-based algorithm for endometrial hyperplasia has not been validated, there has been some suggestion that diagnostics codes alone have low specificity.⁷ To reduce outcome misclassification bias, the Sponsor will develop claims-based endpoint algorithms in which information from the medical record will be used as the ‘gold standard’ to develop predictive models to identify confirmed cases.^{1,8} The process for endpoint algorithm development is described in [Appendix 3](#), and will be completed separately for each of the primary endpoints (i.e., endometrial cancer and endometrial hyperplasia).

7.3.2.2. Secondary Endpoints

Secondary study endpoints include VTE, CHD, stroke, breast cancer, ovarian cancer, thyroid cancer, renal cancer, renal adenoma, gastrointestinal tract cancers, all cancers, and all-cause mortality. The major cardiovascular endpoints are well studied in database research, with multiple validation studies in databases, including the HIRD. In addition, certain cancer

[figure not shown]
endpoints also have been studied. Based on a targeted literature search to identify automated database studies of the endpoints of interest with a focus on validation studies in claims databases, we have identified validated algorithms for the identification of VTE, CHD, stroke, breast cancer and thyroid cancer, which are described in Appendix 3. For secondary endpoints where validated algorithms were not identified, ie, renal cancer, renal adenoma, gastrointestinal cancer and all cancers, algorithms using diagnostic codes have been developed, as shown in Appendix 3.

7.3.3. Fatal Events

Incident safety events that result in either in-hospital or out-of-hospital death will be analyzed. In-hospital events are recorded in the medical claims, while out-of-hospital deaths, including cause of death, will be identified through linkage of the HIRD to the US NDI using patient characteristics such as full name, gender, date of birth, state of residence and (when available) social security number. Potential matches are assigned a probabilistic score based on the strength of the match, and thresholds will be used to identify decedents. The NDI is a national mortality registry for the US. This centralized database of death record information is maintained by the National Center for Health Statistics (NCHS), and contains information on the date and cause of death in the US dating back to 1979. HealthCore will use this registry to identify decedents among patients who have been censored due to disenrollment from their health plan (ie, those patients that potentially could have died) to identify all-cause mortality and fatal events of each primary and secondary endpoint.

NDI data lags real-time by an average of 18-24 months, and is updated once annually. Therefore, the capture of fatal events will lag behind that for nonfatal events. The HIRD and NDI will be linked to ascertain fatal events at two time points. The first will be the earlier of either (a) accrual of at least 3,600 *Duavee* users for whom NDI data are available, or (b) the last study year (i.e., the Final Report). Based on current projections for the uptake of *Duavee* in the US, it is anticipated that the first search will occur in preparation for the Final Report. The second search will be performed in preparation for the mortality supplement to the Final Report to allow for the inclusion of fatal events upon availability of NDI data spanning the full study period (ie, May 2014-May 2018). This is illustrated in Figure 2.

Figure 2. Timing of Mortality Outcome Ascertainment

It is expected that the majority of chronic and ultimately fatal events, such as cancer, will be captured first in the HIRD and any associated fatality with these will be reported some time later in the NDI. Acute fatal events, such as MI or stroke, which may result in death prior to the patient reaching the healthcare system, will only, be captured in the NDI.

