Study design: This PASS is a retrospective cohort study utilizing a US healthcare claims data source (HealthCore Integrated Research DatabaseSM [HIRD]). Two treatment groups of new initiators (*Duavee* and E+P HRT) will be defined and followed for each specified endpoint until the end of the study period or until that endpoint occurs. Other censoring events include hysterectomy, switch of index treatment, and disenrollment from the HIRD, diagnosis of cancer or death. The planned study will be 4 years in duration and will follow new initiators identified in 2014-2018.

Study Population: All patients identified in the HIRD who have received at least one prescription for *Duavee* or E+P HRT since May 2014 (US commercial launch date), and have a baseline period (e.g., 6 or 12 months to be determined by a priori analyses) prior to their first study medicine prescription, will be included in this study. Patients without a uterus and those with an existing cancer diagnosis will be excluded. Only new initiators will be included in the main analysis. To be a new initiator, patients need to have no recorded use of either *Duavee* or E+P HRT products in their baseline period. Patients with prior use of E+P HRT in either the *Duavee* or E+P HRT cohort will be excluded from the main analyses, but will be included in sub analyses. Similarly, patients with a history of unopposed estrogen use in their baseline period will be analyzed in sub analyses but excluded from the main analyses. Figure 4 in [Section 7.7](#) details the analysis populations.

Variables: Variables will be defined and analyzed that represent patient characteristics, comorbidities, utilized medications, medical history, and safety endpoints. A listing of study variables is provided in [Section 7.3.1](#).

Data source: The HIRD is a longitudinally integrated, US research database comprising payment claims for healthcare encounters among included health insurance plans. It is among the largest of its kind in the US and has been extensively used for pharmacoepidemiologic research, including many PASS.^{1,2,3,4}

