7. RESEARCH METHODS

7.1. Study Design

This PASS is a retrospective cohort study utilizing a healthcare claims data source (HIRD) in the US. Two (2) treatment groups (*Duavee* and E+P HRT) will be identified, followed, and reported upon using annual database updates. A new-user cohort design will be used for the main analysis and users with a history of (E+ P) HRT will be examined in sub-analyses. The study will accumulate data for 4 years (May, 2014-May, 2018) as it follows a dynamic cohort of patients that enter the study at different times, based on when *Duavee* or E+P HRT is initiated.

Figure 1 shows the length of study follow-up according to when new users enter the cohort.

The study duration was determined based on sample size calculations, and is the soonest that clinically meaningful HRs for endometrial hyperplasia and endometrial cancer can be detected. Study years and reporting intervals will run from May 1 through April 30 of the next year. Interim (follow-up) and final reports will contain both interval and cumulative data.

All patients in the HIRD who initiate *Duavee* or E+P HRT in the study period (2014-2018) will be considered for inclusion. This PASS is a retrospective cohort study using secondary data. The source data has been accruing since *Duavee* became available in the US in May, 2014. In accordance with EMA Pharmacovigilance Guidance (Module VIII)⁵, the start of a PASS using secondary data is defined to be when the analytic dataset is extracted. This will not be done for this PASS until the study protocol has been approved by the PRAC.

Follow-up will continue from the first use of *Duavee* or E+P HRT through to the earliest of the following censoring events:

- End of continuous health plan eligibility;
- Switch from *Duavee* to an E+P HRT medication or vice-versa;
- (Note: Any use of an estrogen or estrogen-containing product (Appendix 2) that differs from the HRT treatment regimen dispensed on the index date will censor follow-up. This does not include dispensing of a topical estrogen that is a single-unit

E+P HRT. As described in [Section 7.7.4](#), sensitivity analyses exploring the impact of this criterion will be performed.

- First occurrence of a safety endpoint.

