 - Once a patient has had a safety event, they will be censored from the analysis of that event only. For example, a patient for whom an endometrial hyperplasia outcome is identified will remain in follow-up for analysis of breast cancer (and endometrial cancer).
- End of the study period.
 - Patients will be censored by the end of the study period for each interim report and the final study report, however, additional follow-up time for these patients will be added during the subsequent study year.
- Occurrence of any type of cancer diagnosis;
 - As described in [Section 7.7.4](#), sensitivity analyses exploring the impact of this criterion will be performed.
- Hysterectomy;
 - Codes indicating a procedure for hysterectomy will be used to define this censoring criterion.
 - Presence of a code indicating post hysterectomy status (ICD-9-CM V88.01) or a hysterectomy procedure code at any time in the baseline or follow-up period will result in exclusion of the patient. The one exception is, when in the follow-up period, the procedure code precedes the hysterectomy status code (i.e., date of post-index hysterectomy is known); the patient's follow-up will be included, but censored on the procedure date.
- Death.

Discontinuation and/or resumption of *Duavee* or E+P HRT treatment will be defined and recorded, but follow-up will not be censored based on treatment discontinuation. Sensitivity analyses will be conducted to examine the impact of censoring based on (1) treatment switch and (2) cancer diagnosis. The Sponsor will also conduct sub-analyses for patients not included in the main analyses. These patient groups are those with either (1) use of E+P HRT (i.e., not new initiators), or (2) unopposed estrogen in their baseline period.

For each of the 4 study years, the Sponsor will: (1) identify and follow new *Duavee* or E+P HRT users; and (2) extend the follow-up to include newly available data covering any additional follow-up period for patients that were identified during previous study years.

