7.7.4. Sensitivity Analyses

Three sensitivity analyses are planned to explore the impact of censoring due to treatment switch, censoring from analyses of safety endpoints due to occurrence of any cancer type, and potential misclassification of the primary endpoints based on use of the developed algorithms.

Specifically, the main analyses for the primary and secondary endpoints will be performed including person-time after treatment switch, and the main analysis for the primary endpoints only (endometrial hyperplasia and endometrial cancer) will be performed including patients who had been censored due to cancer occurrence. The IR estimate for each primary outcome (endometrial cancer and endometrial hyperplasia) will be corrected for the PPV of the outcome algorithm as identified through validation. This will be done by multiplying the number of observed cases by the PPV point estimate, and will be presented with a 95% CI.

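### As written, all-cause mortality is censored at any cancer diagnosis, so it measures death before a coded cancer; the NDI search wording is a second, lesser barrier

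*Protocol*

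**What the plan says.** Protocol Section 7.1 sets one follow-up rule: "Follow-up will continue from the first use of *Duavee* or E+P HRT through to the earliest of the following censoring events". The list that follows includes "Occurrence of any type of cancer diagnosis". The Abstract repeats it among the other censoring events: "disenrollment from the HIRD, diagnosis of cancer or death". Neither place exempts all-cause mortality, which Section 7.3.2 lists as a secondary endpoint and Section 7.7.1 analyses with its own incidence rate and adjusted HR.

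Under a different bullet, on the first occurrence of a safety endpoint, Section 7.1 states a narrower rule: "Once a patient has had a safety event, they will be censored from the analysis of that event only".

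Section 7.7.4 plans three sensitivity analyses. The one on treatment switch covers primary and secondary endpoints. The one on cancer censoring does not: "main analysis for the primary endpoints only (endometrial hyperplasia and endometrial cancer) will be performed including patients who had been censored due to cancer". The third corrects the primary-endpoint rates for algorithm PPV.

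On deaths, Section 7.3.3 takes in-hospital events from claims and out-of-hospital deaths from the NDI. It describes the search this way: "HealthCore will use this registry to identify decedents among patients who have been censored due to disenrollment from their health plan". It then says of cancers, which it expects to be seen first in the claims, that "any associated fatality with these will be reported some time later in the NDI".

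**The concern.** A woman whose first censoring event is a cancer code leaves the mortality risk set that day, and her later death falls outside follow-up. The endpoint reported as all-cause mortality is then mortality before any coded cancer. The same cut removes fatal CHD, stroke and VTE events that follow a cancer diagnosis.

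Section 7.3.2 includes all-cause mortality to put fatal safety events in context, and several of the safety endpoints are cancers. A mortality supplement is planned about two years after the final report for death endpoints over the full study period. If *Duavee* and E+P HRT differed in deaths that follow a cancer diagnosis, the all-cause HR in that supplement would not show it.

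**Working it through.** **Step 1: which rule governs all-cause mortality.** The any-cancer bullet in 7.1 stands in a list that ends follow-up in general. The narrower rule stands under a separate bullet, and its worked example is endometrial hyperplasia, which is not a cancer. Section 7.7.4 describes the cancer rule as censoring from analyses of safety endpoints, which supports the broad reading. So the literal rule censors all-cause mortality at cancer. Breast, ovarian, thyroid, renal and gastrointestinal cancers and any cancer are themselves safety endpoints, however, so for them the two bullets give different answers.

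**Step 2: whether a planned analysis restores these deaths.**
- Main analysis: no, by step 1.
- Treatment-switch sensitivity analysis: it covers secondary endpoints but lifts only switch censoring.
- Cancer-censoring sensitivity analysis: it lifts the rule for hyperplasia and endometrial cancer only.
- PPV correction: it concerns the primary-endpoint rates only.

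None restores deaths after cancer to all-cause mortality or to fatal CHD, stroke or VTE.

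**Step 3: what the NDI wording adds.** Under the earliest-event rule, a woman with a cancer code is censored for cancer even if she later leaves the plan. Read literally, she is not in the NDI search group. This is secondary. An in-hospital death would be visible in claims and still not count, and a wider NDI search alone would not bring her death inside follow-up. Changing the censoring without the search would leave out-of-hospital deaths unidentified.

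**Step 4: what is not lost.** Section 7.7.1 analyses fatal endpoints as composites of the non-fatal event and the cause-specific death. A woman with breast cancer is already an event at diagnosis for breast cancer and for any cancer. Only her later contribution to all-cause mortality and to the non-cancer fatal endpoints is lost.

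**Step 5: size.** The protocol states no death count, mortality rate or mortality precision, so there is no figure to reproduce. As an illustration, let p be the share of comparator deaths that follow a coded cancer and c the HR on those deaths, with HR 1.0 on all others. Then

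true all-cause HR = (1 − p) × 1.0 + p × c.

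Censoring at cancer leaves only the other deaths, so the analysed HR is about 1.00. Both p and c are assumptions.

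| p | Deaths kept per 100 | True HR, c = 1.5 | True HR, c = 2.0 | As analysed |
|---|---|---|---|---|
| 0.1 | 90 | 0.9 + 0.15 = 1.05 | 0.9 + 0.2 = 1.10 | about 1.00 |
| 0.3 | 70 | 0.7 + 0.45 = 1.15 | 0.7 + 0.6 = 1.30 | about 1.00 |
| 0.6 | 40 | 0.4 + 0.9 = 1.30 | 0.4 + 1.2 = 1.60 | about 1.00 |

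**The case against.** The best reply is that the protocol does not clearly intend this. Its event-specific rule, applied to the cancer endpoints, would keep a breast cancer case at risk for death. Section 7.3.3 expects cancer fatalities to appear in the NDI and says the NDI serves all-cause mortality and the fatal events of every endpoint. It also glosses the search group as the women who could have died, which could be taken to include a cancer patient who later leaves the plan. This stands in part: the document is contradictory rather than uniform. But no sentence exempts mortality from the any-cancer bullet, and 7.7.4 limits its relief to the primary endpoints right beside an analysis that covers secondary endpoints too.

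The second reply is that the effect may be small. Women with cancer at baseline are excluded. Pilot E+P follow-up averages 89,438 / 50,350 ≈ 1.8 person-years per user, and Section 7.9 notes long cancer latency. This stands: p could lie at the low end of the range, where the true HR is 1.05-1.10.

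The third reply is that all-cause mortality is a contextual secondary endpoint in an estimation study. This also stands, and it limits the severity.

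A reader might go further and infer that deaths after cancer are never counted anywhere, or that a cancer excess could not show at all. The documents do not support either. Cancer cases count at diagnosis in their own composites. For the primary endpoints, 7.7.4 readmits women censored for cancer, although the fatal part is complete only if the NDI search reaches them.

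**Conclusion.** The point holds for all-cause mortality and for the fatal part of CHD, stroke and VTE. As written, deaths after a coded cancer are absent from these in the main and every planned sensitivity analysis. Cancer censoring is the main cause and the NDI wording the secondary one. Both conflict with the protocol's own expectation of later NDI capture, and the any-cancer bullet sits uneasily with the event-specific rule in 7.1.

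The direction of the problem, a hidden difference in deaths that follow cancer, follows from the rules. Its size does not: the contrast of 1.05-1.60 with about 1.00 rests wholly on the assumed p and c and on HR 1.0 for other deaths. It should not be read as a predicted bias. Treatment-switch censoring is not part of the fault, because a sensitivity analysis already lifts it for all endpoints. Primary-endpoint conclusions are unaffected, so this is a moderate point rather than one that must be fixed before the study can proceed.

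**What to change.** 1. In Section 7.1, state the censoring events endpoint by endpoint. Do not censor all-cause mortality, or the fatal non-cancer endpoints, at a cancer diagnosis. At minimum, extend the cancer-censoring sensitivity analysis in 7.7.4 to the secondary endpoints, including all-cause mortality.
2. In Section 7.3.3, search the NDI for every cohort member whose enrolment ended, whatever censored her first.
3. State through what date an NDI death after disenrollment counts. Disenrollment is itself a censoring event in 7.1. A footnote in Section 4 ends mortality follow-up in May 2018 but does not say whether a woman who left the plan earlier stays at risk until then.
4. Reconcile the any-cancer bullet and the event-specific rule in 7.1 with 7.3.3 and 7.7.4.

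The cost is protocol wording, a longer NDI search file and some added analysis, with no new data source. It should be settled before the NDI linkages, because a restricted search file would leave these deaths unidentified.
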